Frailty will be measured by performance on the Fried Frailty Index. This assessment includes the following criterion: patient's weight, exhaustion level, physical activity, walking speed, and hand grip strength. Patients will be asked if they have experienced unintentional weight loss of more than 10 lbs, in the past year. Patients will rate the following 2 statements from 0-3; "I felt that everything I did was effort" and "I could not get going". Additionally, patients will be asked "How often in the last week did you feel this way?". Patients will answer questions regarding which activities that participated in within the last month. Patients will complete a 15-second 'get up and go' test in which their walking speed will be measured. Lastly, patients will complete a hand grip strength test using a hand held dynamometer.

Additional assessments will include measures of clinical outcomes, physical activity, sleep, quality of life, and coping and self-efficacy, social support and health habits.

- 1. The main clinical/medical endpoint will be a composite measure of CLAD-free survival (CLAD and all-cause mortality). Patients' medical records will be reviewed semi-annually and within 3-weeks following the anniversary of each patient's baseline study assessments. Patients are followed closely by each of the enrolling transplant centers for their lifetime after lung transplantation facilitating accurate assessment of these medical events. Events will be adjudicated by our pulmonologists using standard criteria for CLAD. Data with regards to survival, re-transplant, and CLAD are maintained accurately at each center and reported regularly to the United Network of Organ Sharing (UNOS). Records of outside hospitalizations are incorporated into the electronic record of the enrolling center. We will use information from a range of sources to populate a secure Redcap database
- (https://redcap.duke.edu/redcap/) with clinical follow-up forms. If the patient is no longer being seen at Duke, we will acquire their records from their local pulmonary provider; death data are available to the respective transplant programs through the UNOS. Documentation of patient mortality will include verification through the acquisition of hospital and Emergency Medical Services records.

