Participant compensation will total \$300 each for the 180 randomized participants. Payments will occur in installments and include the following: \$25 for screening, \$75 for completion of baseline assessments, \$100 for completion of the 3-month intervention, and \$100 for the 1-year follow-up visit.

Risk/Benefit Assessment

The primary risks of this study are minimal and are primarily associated with confidentiality. There is some risk attendant to confidentiality of self-report data. In order to ensure confidentiality of data, all records will be identified by the patient's identification number, not by name. All raw data will be kept in a locked file cabinet. Although several previous psychosocial interventions may be associated with increased risk, we believe that it is unlikely that this treatment will be harmful to patients. Nevertheless, we will carefully monitor symptoms and refer those patients with high levels of depression or distress for treatment.

All patients enrolled in the study will continue to take all of their prescribed medications. The risk of serious injury due to study participation is negligible. All measurement techniques have been used extensively by the investigative team without a single adverse event. Nonetheless, we are aware that the lung transplant recipient can be characterized by unstable health. Procedures for protecting subjects against potential risks include screening procedures, a brief physical examination by the study pulmonologist who also will be available to attend to any acute medical issues when patients are in treatment with the interventionists. Patients possibly requiring immediate medical care will be contacted for further evaluation by members of the research team who also may be their healthcare providers at the transplant clinics in the DUMC. However, study personnel will not be involved in the ongoing medical care of participants. Patients will be referred to their local physicians when needed.

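### No masking to arm is described for CLAD adjudication by the study's own pulmonologists, so the judged part of CLAD-free survival is open to bias

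*Combined protocol and SAP*

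**What the plan says.** All references are to the combined protocol and SAP.

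- **Endpoint.** Design & Procedures, additional assessments, item 1: "The main clinical/medical endpoint will be a composite measure of CLAD-free survival (CLAD and all-cause mortality").
- **Who judges it.** Same item: "Events will be adjudicated by our pulmonologists using standard criteria for CLAD". The adherence section also speaks of study pulmonologists in the plural, so the natural reading is adjudication by the study team. Deaths, by contrast, are verified from hospital and emergency-service records.
- **Contact with participants.** Risk/Benefit Assessment: the safeguards include "a brief physical examination by the study pulmonologist", a person described as one "study pulmonologist who also will be available to attend to any acute medical issues when patients are in treatment with the interventionists". Patients who may need immediate care are contacted by "members of the research team who also may be their healthcare providers at the transplant clinics in the DUMC".
- **Limit on contact.** The next sentence reads: "However, study personnel will not be involved in the ongoing medical care of participants".
- **Status of the endpoint.** Data Analysis & Statistical Considerations lists medical outcomes (CLAD) among the secondary outcomes. Its power paragraph calls the effect on clinical outcomes an exploratory aim.

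The text available does not mention masked adjudication, an independent events committee, removal of arm information before review, or separation of adjudicators from those who see participants.

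**The concern.** The two programmes differ openly. CSTEX gives coping training and coached exercise, and SOC-ED gives education. Participants will know what they receive and may tell their clinicians. With such an intervention, masking the adjudicator is the practical protection for an endpoint that needs judgement.

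Death needs little judgement. CLAD does, both on whether it is present and, for a time-to-event analysis, on when it began. If the person deciding knows the arm and belongs to the team testing CSTEX, borderline cases can be read differently in the two arms without any intent. A favourable CLAD-free survival result would then face the objection that the team judged its own events, and nothing in the stated procedure would answer it.

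**Working it through.** **Step 1. Could an adjudicator know the arm?** The endpoint item assigns adjudication to the study's pulmonologists. The Risk/Benefit Assessment gives two routes by which a study pulmonologist might learn the arm after randomisation: attending an acute problem during treatment, and being the patient's transplant-clinic provider. The brief physical examination is a poor third route. It is listed with the screening procedures and probably comes before randomisation. The stated procedure therefore allows arm-aware adjudication but does not require it.

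**Step 2. How large could the effect be?** The plan has no figure on this point to reproduce, so what follows is an illustration.

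Inputs from the power paragraph:
- control event rate p_C = 0.75;
- 75 patients per group;
- alpha 0.05 (taken as two-sided, since the plan does not say).

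Assumptions not in the documents:
- no true effect;
- CLAD makes up a share c = 0.50 to 0.70 of composite events;
- a fraction m = 0.05 to 0.10 of CLAD events is not called, in CSTEX only;
- proportional hazards.

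Formulas:
- observed CSTEX event rate: p_T = p_C × (1 − c × m);
- apparent hazard ratio: HR = ln(1 − p_T) / ln(1 − p_C), with ln(0.25) = −1.386;
- rejection rate under no true effect: Φ(−1.96 − d) + Φ(−1.96 + d), with d = √(events/4) × ln(HR) and events = 75 × (p_C + p_T).

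| c | m | p_T | Apparent HR | Two-sided rejection rate |
|---|---|---|---|---|
| 0.50 | 0.05 | 0.731 | 0.95 | 5.9% |
| 0.50 | 0.10 | 0.712 | 0.90 | 8.6% |
| 0.70 | 0.05 | 0.724 | 0.93 | 6.8% |
| 0.70 | 0.10 | 0.698 | 0.86 | 12.0% |

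Last row in full:
- p_T = 0.75 × (1 − 0.07) = 0.6975;
- HR = ln(0.3025)/ln(0.25) = 0.86;
- events = 75 × 1.4475 = 108.6;
- d = √27.1 × ln(0.8625) = −0.77, which gives a rejection rate of 12.0%.

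**Step 3. How sensitive is this?**
- With a 25% event rate and the same c and m, the HR runs from 0.97 to 0.92 and the rejection rate from 5.1% to 5.7%.
- With m = 0.20 at the 75% event rate, the HR runs from 0.81 to 0.75 and the rejection rate from 19% to 32%.
- If the missed events were in SOC-ED instead, the ratios in the table invert: 1/0.948 = 1.05 to 1/0.862 = 1.16.
- The table treats a patient with missed CLAD as event-free. One who later dies in follow-up still counts, only later, so the bias would be smaller.

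**The case against.** The strongest case on the other side has five parts.

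1. **Silence is not a statement.** A reader might infer that adjudicators will be unmasked. The documents do not say so. They do not address masking at all, and one stretch of text, between the assessment list and the compensation paragraph, was not available to check. This stands: the supportable claim is that no masking is described.
2. **Same person.** A reader might infer that the pulmonologist who attends acute problems is the one who adjudicates. The endpoint item uses a plural and the Risk/Benefit Assessment a singular, and nothing joins them. The overlap is possible, not stated.
3. **Weak route to the arm.** Sessions in both arms are telephone calls, and the pulmonologist is only on hand for acute problems, so this would affect few patients. A reader might also note that the word interventionist is used for CSTEX staff and educator for SOC-ED staff, and conclude that being called in reveals the arm. The protocol also calls SOC-ED an intervention, and the safety text concerns patients generally, so the word cannot carry that weight. The clinic-provider route remains.
4. **Contradiction on care.** A reader might see the statement that "study personnel will not be involved in the ongoing medical care of participants" as contradicting the sentence before it. It opens with a contrast word and can be read as a qualification: acute evaluation by the team, but no ongoing care. It needs clarifying, but it is not a proven contradiction.
5. **Existing safeguards.** Standard CLAD criteria, scheduled record review, centre data reported to the national organ-sharing network, and pulmonary function testing to professional guidelines all narrow discretion. This stands, but none of them hides the arm.

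A larger illustration is also tempting: dropping 5% to 10% of all CSTEX events gives 0.75 × 0.95 = 0.7125 and 0.75 × 0.90 = 0.675, or hazard ratios of 0.90 and 0.81. That removes deaths as well as CLAD events, and deaths are not the exposed component.

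**Conclusion.** The concern holds in a limited form. The plan has CLAD adjudicated in-house, allows study pulmonologists and research-team members to have contact that could reveal the arm, and describes nothing in the available text to keep adjudicators masked. The CLAD component of CLAD-free survival is open to bias for that reason.

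Under the stated assumptions, an apparent hazard ratio of about 0.95 to 0.86 could arise with no true effect. The false-positive rate would be 5.9% to 12.0% instead of 5%. At a low event rate the effect is close to nil, and at heavier differential reading it is material. Neither the size nor the direction of differential reading comes from the documents, so the figures show what is possible and do not estimate what will happen.

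A reader might go further and doubt the trial's main conclusion. The documents do not support that. The composite is secondary or exploratory, its mortality component is not exposed, and the primary distress endpoint comes from questionnaires that CLAD adjudication does not touch. This is an inexpensive improvement worth making.

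**What to change.** - **Design & Procedures, additional assessments, item 1.** State that CLAD presence and onset date are adjudicated masked to arm, from record packets with any arm-identifying information removed. The adjudicator should be a pulmonologist already on the team who, where possible, has had no post-randomisation contact with that participant. The qualifier is needed because the documents do not say how many pulmonologists are available. If masking is already practised, one sentence saying so settles this part.
- **Risk/Benefit Assessment.** Clarify how the statement that research-team members may be patients' clinic providers fits with the statement that study personnel are not involved in ongoing care. The two passages need to be reconciled. Which arrangement is right is for the study team to say.

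The cost is coordinator time to prepare packets and assign cases among the pulmonologists. Events not yet adjudicated can be handled this way without any change to data collection.

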Participant compensation will total \$300 each for the 180 randomized participants. Payments will occur in installments and include the following: \$25 for screening, \$75 for completion of baseline assessments, \$100 for completion of the 3-month intervention, and \$100 for the 1-year follow-up visit.

Risk/Benefit Assessment

The primary risks of this study are minimal and are primarily associated with confidentiality. There is some risk attendant to confidentiality of self-report data. In order to ensure confidentiality of data, all records will be identified by the patient's identification number, not by name. All raw data will be kept in a locked file cabinet. Although several previous psychosocial interventions may be associated with increased risk, we believe that it is unlikely that this treatment will be harmful to patients. Nevertheless, we will carefully monitor symptoms and refer those patients with high levels of depression or distress for treatment.

All patients enrolled in the study will continue to take all of their prescribed medications. The risk of serious injury due to study participation is negligible. All measurement techniques have been used extensively by the investigative team without a single adverse event. Nonetheless, we are aware that the lung transplant recipient can be characterized by unstable health. Procedures for protecting subjects against potential risks include screening procedures, a brief physical examination by the study pulmonologist who also will be available to attend to any acute medical issues when patients are in treatment with the interventionists. Patients possibly requiring immediate medical care will be contacted for further evaluation by members of the research team who also may be their healthcare providers at the transplant clinics in the DUMC. However, study personnel will not be involved in the ongoing medical care of participants. Patients will be referred to their local physicians when needed.

We also will take special precautions to ensure the safety of patients with clinically significant depression, i.e., patients with BDI-II scores >29 (moderate-severe depression) or who are actively suicidal. Although we are not pre-selecting transplant recipients based upon their level of distress or depressive symptoms, our assessments may determine the presence of significant clinical depression. In the unlikely event that patients are determined to be actively suicidal, they will be queried for suicidal plans, intent and past suicidal behaviors. Those with current active suicidal ideation, history of suicidal acts within the past 12 months, or bipolar disorder or psychosis will not be enrolled in the study and appropriate referral or admission procedures will be initiated. If a patient exhibits moderate-severe depression (e.g., BDI-II >29) at baseline, we will inform the participant and, with his or her permission, notify the treating pulmonologist. During the 12-week treatment phase, any patient who is determined to be actively suicidal over the course of the trial will be referred for psychiatric evaluation and possible hospital admission. If they are found to be at immediate risk, emergency procedures will be followed including requesting an ambulance to take the patient to the emergency department (ED) for immediate evaluation and treatment.

This study has several potential benefits. First, patients receiving CSTEX may learn coping skills that may significantly decrease symptoms of distress, improve their quality of life, and potentially reduce their pulmonary-related hospitalizations and increase their survival. Second, patients in SOC-ED may benefit from a better understanding of their condition and its management. Third, this study will also explore individual differences that may be related to improvements in distress and clinical outcomes. For example, older patients, women, or patients with a particular native disease may be more likely to benefit from treatment. This may make it possible to identify lung transplant patients who are most likely to respond well to CSTEX.

If a potential participant chooses to not participate, information on exercise and coping mechanisms can be acquired through their pulmonologist or staff from the PR program.

Data Analysis & Statistical Considerations

The primary endpoint will be a global measure of distress. Secondary outcomes will include measures of functional capacity, coping, self-efficacy, PA, health behaviors, frailty, and medical outcomes (i.e., CLAD), the latter of which will be documented by annual follow-up visits of up to 4 years (median >2 years).

All analyses will follow the intention-to-treat (ITT) principle, including all patients who were randomized. Patterns of missing data will be characterized using Rubin's criteria and managed accordingly using Harrell's multiple imputation (mult.impute) procedure in R. We will supplement the ITT analysis with an examination of the treatment effect among completers using Rubin's Complier Average Causal Effect (CACE) model.

We will test our primary hypotheses using the "gatekeeper" approach, which has been shown to maintain the experiment-wise error rate while maximizing power when testing multiple endpoints. This type of methodology has been widely advocated in RCTs involving medical populations as a parsimonious strategy to control type-I error within the first (i.e. "gatekeeper") step, because a favorable result on any individual component observed by chance is unlikely to be overly influential to the composite as a whole. Because the type-I error is minimized at this stage of analysis, the familywise error rate can then be propagated to the second analysis stage, examining individual components. In contrast, error correction to individual components of the composite often over-controls for type-I error when the purpose is explanatory. In order to mitigate Type-I error with multiple outcomes, we will partition the conventional alpha = .05 to test treatment effects on Global distress and Functional capacity each at alpha = .025. Thus, for our examination of global distress changes, an experiment-wise p-value of .025 will be used to assess significance. If this test fails to be rejected at p-value < .025, then tests of individual components are not interpreted. However, if improvements in global distress are found, examination of changes in individual components of distress are carried out in a secondary, explanatory step. Consistent with contemporary recommendations, secondary outcomes will be considered as potentially supportive and therefore examined at the alpha = .05 for each domain.

With respect to changes in global distress, we estimated power using a correlation of 0.53 between covariates and the outcome, an initial sample size of 150 participants (amended to up to 180 participants), attrition of 15%, and an alpha of 0.025. Based on these assumptions, we will have 80% power to detect a small-to-moderate treatment size difference (d = 0.44), comparable to what we observed in our prior work among pre-transplant candidates. For changes in functional capacity and PA, we should have 80% power to detect even small differences in 6MWD (d = 0.21) and total daily actigraphy steps (d = 0.32). As an exploratory aim, we also will examine the impact of CSTEX on clinical outcomes. Power for our exploratory clinical event models was estimated assuming a conservative event rate of 75% in the control group, 42 months for patient accrual, a median follow-up of 30 months and a minimum follow-up time of 6 months. At an alpha of 0.05, and 75 patients per group, we will have

80% power to detect a 64% event rate reduction. We will carefully examine all model assumptions and reparameterize as indicated. All analyses will be carried out using SAS (Cary, NC) or R (http://cran.r-project.org/) software.

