Previous RCTs have demonstrated that behavioral interventions are effective in reducing distress and improving psychological QoL in patients with lung disease, including pre-transplant patients. We previously demonstrated that coping skills training (CST), delivered to wait-listed, pre-lung transplant candidates was effective in reducing psychological distress and depression, as well as improving psychological QoL, and that improved coping and reduced distress mediated the beneficial effects of treatment. Similar benefits from CST were observed for COPD patients.

Exercise interventions also have been shown to reduce distress and improve depressive symptoms in a variety of clinical populations, including individuals with cardiovascular disease, heart failure, and COPD. Furthermore, there is growing evidence that exercise may be comparable to the benefits of antidepressant medications in reducing depressive symptoms and has the additional benefit of improving physiological biomarkers, which may improve long-term survival.

Despite evidence that exercise improves muscle strength and functional capacity in post-lung transplant patients, to our knowledge, no study has examined the impact of exercise on distress, psychological QoL, and medical outcomes in lung transplant recipients. In a study of COPD patients, we reported that greater levels of PA were associated with lower levels of depression, and that the relationship between elevated depressive symptoms and greater risk of adverse clinical events was mediated by low levels of PA. In addition, we found the improvements in functional status and PA were associated with improved event-free survival, independent of traditional clinical risk markers. These findings suggest that exercise may play an important role in improving functional capacity, increasing PA, and reducing distress, and that these improvements may result in clinical benefits among individuals with advanced lung disease.

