The CSTEX intervention will consist of 12, 30 min weekly sessions conducted by respiratory therapists knowledgeable about lung transplantation and trained in motivational interviewing (MI), Cognitive Behavioral Therapy (CBT), and exercise therapy. Consistent with social cognitive theory, initial sessions are designed to target daily exercise and focus on improving exercise self-efficacy by providing a rationale for exercise, instruction and goal setting (i.e., exercise prescription), identification and management of barriers to exercise, and assessment and reinforcement of exercise participation.

Each weekly session will be delivered via a telephone call to the study participant from the interventionist. This method decreases the burden associated with in-person appointments, eliminates travel expenses for patients living in rural areas, and permits outreach to individuals who may be less receptive to traditional mental health services.

Patients in the CSTEX group will also receive a Fitbit fitness wristband to self-monitor their activity levels. They will be asked to wear the Fitbit daily during the 12-week intervention, from rising in the morning until bedtime, when they will recharge the device overnight. Patients will download the Fitbit app onto their smartphone, allowing the Fitbit to transfer each patient's daily activity data to the Dashboard on the app. The interventionist will be able to monitor participants' exercise and physical activity remotely through the Fitbit Dashboard portal and will incorporate this information in their weekly sessions. Participants also will have access to the Dashboard so they will be able to self-monitor their performance. Fitbit data will be reviewed during each session and any issues will be addressed before addressing the scheduled topic area.

The standard home-based exercise prescription for post-transplant patients is identical to the current recommendations for adults and includes frequency, intensity, and duration – 30 minutes of moderate-vigorous intensity aerobic exercise (e.g., walking), 3-5 days/week for a total of 150 minutes each week.

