This may be an aspirational goal that may not be realistic for all participants, so exercise prescriptions will be individualized based on their baseline activity levels, 6-minute walk distance, and resting heart rate (HR). For most participants, the aerobic exercise prescription will consist of 30 minutes of aerobic exercise at least 3 days/week at an intensity of 4-6/10 ('sort of hard' to 'hard') on the Modified Borg Rating of Perceived Exertion Scale, corresponding to a HR >60% max. These 30 min bouts of moderate-vigorous (MVPA) intensity exercise can be partitioned into several 10-15 min bouts per day or a single 30-min session.

As participants demonstrate self-mastery of exercise-related behavioral goals, the intervention focus will transition to emphasize elements of self-management theory. Coping skills to aid in the management of distress include training in relaxation techniques, cognitive restructuring, and problem solving. When indicated, relaxation and cognitive restructuring will be applied to the management of unpleasant physiological responses to exercise and problem solving strategies will be used to address barriers to exercise.

The SOC-ED condition provides support and enhanced post-transplant education. Patients in SOC-ED will also receive 12, 30 minute weekly telephone calls between the study participant and study educator. Patients in this group will be given detailed educational information about post-transplant care, the importance of medication adherence, and maintenance of physical activity. The calls will be conducted by trained staff knowledgeable about transplantation and skilled in educational instruction. The study educator will assist patients with self-management but they will not instruct patients in coping strategies or provide physical activity feedback. However, participants randomized to the SOC-ED intervention also will be provided with a Fitbit fitness wristband to self-monitor their own activity levels.

The telephone calls may be audio-recorded for training and quality control. The recorded sessions will be stored on a secure Duke server and only accessible to study key personnel. The recordings will be erased at the earliest possible time or by the end of the study.

Patients in both groups will be able to keep the Fitbit activity monitor. Randomized participants will also receive a t-shirt with the study logo.

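### Does the undefined term completer in the supplementary CACE analysis call for a change to the plan?

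*Combined protocol and SAP*

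**What the plan says.** Data Analysis & Statistical Considerations makes ITT on all randomised patients the main analysis and handles missing data by multiple imputation. One sentence then undertakes to "supplement the ITT analysis with an examination of the treatment effect among completers", and names Rubin's CACE model as the method. Nothing further is said about this analysis, apart from a general promise at the end of the section: "We will carefully examine all model assumptions and reparameterize as indicated".

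Elsewhere, Design & Procedures offers 12 weekly 30-minute contacts in CSTEX, and for the control arm: "Patients in SOC-ED will also receive 12, 30 minute weekly telephone calls between the study participant and study educator". No minimum number is set in either arm. The text available for this review mentions finishing the intervention in two other places. One is a payment "for completion of the 3-month intervention", in the compensation paragraph just before Risk/Benefit Assessment. The other is the post-intervention survey of perceived change (item 8 of the additional assessments). Neither says what counts as finishing. The adherence measures in the plan cover the medical regimen and medication, not session attendance.

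**The concern.** Completer could mean all 12 sessions, some lower number, reaching week 12, or having the 12-week assessment. Each reading gives a different completer share. In the simplest CACE estimator that share is the denominator, so the same data yield different effect sizes. If the definition were fixed after unblinding, a reader could not tell whether the result had influenced it.

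Three further points add to the unease:

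- Both arms have 12 calls, so it is not stated whether compliance is a CSTEX matter only.
- The sentence runs together observed completers, a group selected after randomisation, and compliers in the CACE sense. The latter are compared with the control patients who would have complied.
- A strict threshold combined with an exclusion restriction assumes no effect in partial attenders. The plan says of CSTEX that "initial sessions are designed to target daily exercise and focus on improving exercise self-efficacy", and in Background & Significance that "Exercise interventions also have been shown to reduce distress and improve depressive symptoms in a variety of clinical populations". A patient who stops early might therefore still have gained something.

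At stake would be the size of the effect claimed for patients who took the treatment.

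**Working it through.** The plan gives no figure for the CACE analysis, so there is none to reproduce. The check asks what the missing definition could change.

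**Inputs.** From the power paragraph of Data Analysis & Statistical Considerations: d = 0.44 detectable with 80% power at alpha .025. I take the test as two-sided, which the plan does not state. The completer shares c are assumptions.

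**Standard error implied by the power statement.** SE = 0.44 / (2.24 + 0.84) = 0.44 / 3.08 = 0.143.

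**Ratio estimator.** CACE = ITT / c. With c treated as known, SE(CACE) = SE(ITT) / c.

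| c | Estimate 0.44/c | SE 0.143/c | 95% interval | Estimate/SE |
|---|---|---|---|---|
| 0.95 | 0.46 | 0.150 | 0.17 to 0.76 | 3.08 |
| 0.85 | 0.52 | 0.168 | 0.19 to 0.85 | 3.08 |
| 0.70 | 0.63 | 0.204 | 0.23 to 1.03 | 3.08 |

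The strictest estimate exceeds the loosest by 0.629/0.463 = 1.36, which is simply 0.95/0.70. The intervals overlap heavily and the last column does not move, because c cancels. Estimating c from the data adds variance terms that are multiplied by the ITT effect. They vanish when that effect is zero, so they give no route from a null ITT result to a positive CACE.

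**Sensitivity to the SE.** Rebuilding it from the stated inputs (150 patients, 15% attrition, so 63.75 per arm; correlation 0.53, so residual SD √(1 − 0.53²) = 0.848) gives 0.848 × √(2/63.75) = 0.150. Power at 0.44 is then about 75% rather than 80%. Estimate/SE becomes 0.44/0.150 = 2.93, again the same for every c.

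**Partial attenders.** Let q be the share of partial attenders and f their effect as a fraction of the completers' effect, with no effect in non-attenders. Then the estimate divided by the true completer effect is 1 + qf/c.

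- c = 0.85, q = 0.15: f = −0.25, 0, 0.5, 1 gives −4%, 0%, +9%, +18%.
- c = 0.70, q = 0.30: the same f gives −11%, 0%, +21%, +43%.

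The range includes zero and has no fixed sign. It also needs a strict threshold, an imposed exclusion restriction and a non-zero f, none of which the plan states. The plan's own content points both ways. Exercise comes first, but the part aimed squarely at distress comes later: "Coping skills to aid in the management of distress include training in relaxation techniques, cognitive restructuring, and problem solving". SOC-ED patients also receive a Fitbit and activity education, so f may be small or zero.

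**Which reading is natural.** The plan names the CACE model, and that settles the group: compliers as CACE defines them, not a bare comparison of observed completers. Design & Procedures says the study educator will not teach coping strategies or give activity feedback, so control patients have no access to CSTEX. Defining compliance by CSTEX attendance is therefore the obvious default. The classing of partial attenders follows once a threshold is set. The ratio can be computed in each imputed data set and pooled in the usual way.

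**The case for a change.** The strongest reply is that a prespecified analysis ought to be specified, and that the spread could be much wider than 36%. If attendance is modelled as beta-binomial with a mean of 85% of 12 sessions (parameters summing to 3, an assumption), a threshold of 6 gives a 94% completer share and an estimate of 0.47. A threshold of 10 gives 73% and 0.61, and requiring all 12 gives 44% and 1.00. With mean attendance of 75%, requiring all 12 leaves 24% and an estimate of 1.82. Moreover, CACE names a framework and an estimand. Instrumental-variable, likelihood and Bayesian mixture fits all belong to it under different assumptions, and the cancellation shown above belongs to the ratio estimator. If completion meant having the 12-week assessment, it would also overlap with the missing data that imputation is meant to handle.

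Some of this stands. The definition is absent, the point estimate depends on it, and other estimators need not leave the test unchanged. But the extreme estimates carry equally inflated uncertainty: at 24%, SE = 0.143/0.242 = 0.59 and the 95% interval is about 0.66 to 2.97. A report that gives the completer share lets any reader multiply back to the ITT effect. These are different estimands on the same data, not errors. An any-session definition, or session count instrumented by randomisation, would not clearly be better. The first approaches ITT if nearly everyone takes one call. The second assumes equal benefit per session although the content changes over the course.

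**Conclusion.** The gap is real but small, and no change to the plan follows. No stated rule gives a wrong answer; a supplementary analysis is described briefly, and whoever runs it has to settle the threshold, the arm and the fitting method. The plan's naming of CACE and its description of the two arms point to a sensible default.

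On the assumed completer shares of 70% to 95%, the definition moves the supplementary estimate between 0.63 and 0.46 and leaves the ratio of estimate to standard error at about 3.1. That holds for a ratio estimator with the share treated as known, with d = 0.44 taken as the ITT effect and a two-sided .025 level. The possible bias from partial attenders, −11% to +43% across the cases examined, rests on premises the documents do not contain and has no established direction. The primary ITT comparison, its alpha, the gatekeeping step and the sample size do not depend on any of this.
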